##### 3.2.2 SECONDARY ENDPOINTS

Endpoint	Start	End
1. Localized control rate: Incidence of progressive disease within or at the planned tumor volume (PTV) margin		Time of progression, transplantation, death or 2-years after last SBRT dose, whichever occurs first.
2. Incidence of intrahepatic progressive disease		
3. Incidence of extrahepatic progressive disease		
4. Proportion of participants that proceed to transplantation	First dose of SBRT	
5. Overall Survival		Time of death or 2-years after last SBRT dose
6. Incidence of non-classic RILD, defined as grade 4 aspartate aminotransferase or alanine aminotransferase elevation, or an increase in CP score of $\geq 2$ within 1 week to 3 months after completing SBRT (Appendix A)		3 months after last SBRT dose

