#### 6.1.6 ADVERSE EVENT EVALUATION

Toxicities and adverse experiences will be assessed at each visit using the [CTCAE v5.0](#) and quantifying current Child-Pugh score to assess risk of RILD. Adverse events will be monitored from the time the participant signs the Consent Form up until 3 months following SBRT. Participants will be instructed to report all AEs during the study and will be assessed for the occurrence of AEs up until 3 months following radiation therapy. All AEs (serious and non-serious) must be recorded on the source documents and CRFs regardless of the assumption of a causal relationship with the study therapy.

For details on AE collection and reporting, refer to Section 8.6.

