#### **6.7 UNSCHEDULED VISITS**

Unscheduled study visits may occur at any time if medically warranted. Any assessments performed (e.g., laboratory or clinical assessments) at those visits should be recorded in the CRF.

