## 6.8 SCHEDULE OF EVENTS

Visit Days	Screening	Treatment					Follow-Up B (±4 weeks)	
	Days -28 to -1	Days † (+7 days)						
		1	3	5	7	9*		
SBRT A		X	X	X	X	X		
Informed consent	X							
Inclusion/exclusion criteria	X							
Medical history	X						X B	
Prior/concomitant medications	X						X B	
Physical Examination C	X						X B	
Radiographic Imaging	X	X D	X D	X D	X D	X D	X E	
Hematology F	X						X B	
Biochemistry G	X						X B	
Coagulation	X						X	
Pregnancy test	X							
Fiducial placement (if needed)	X							
AE assessment	X	X					X	
EORTC QLQ-30	X						X B	
FACT-Hep	X						X B	

† Starting on day 1, SBRT dose fractions are given every other day (i.e., Monday-Friday), but not administered on Saturdays, Sundays, or holidays. Dosing interruptions because of weekends and holidays will be recorded in CRF.

\*Day 9 study assessments of radiographic imaging and AE collection will serve as Early Termination and/or End of Treatment Visit.

A Scheduled SBRT visits may be delayed by no more than 7 days between each visit, or may occur earlier than scheduled by no more than 3 days.

B Follow-up assessment to occur 6 weeks following completion of SBRT then every 3 months up to 2 years post SBRT therapy

C All physical exams will include assessing weight, vital signs, and ECOG performance status. Height will be measured at screening visit only.

DCone-beam CT will be obtained prior to each SBRT fraction.

E Participants will undergo surveillance imaging (e.g., CT scan) 6 weeks following completion of SBRT and then every 3 months for the first 2 years.

F Hemoglobin, platelets and white cell count with differential white count

G Biochemistry to include renal (creatinine, urea, sodium, potassium) and liver function (AST, ALT, bilirubin)

HAEs and laboratory safety measurements will be graded per NCI CTCAE version 5.0 as well as definition of radiation-induced liver disease (Child-Pugh elevation of 2 or more). All AEs, whether gradable by CTCAE or not, will also be evaluated for seriousness. Record all AEs and SAEs occurring from the time of consent signing to 3 months following the completion of SBRT.

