#### 9.2.3 ANALYSIS OF THE SECONDARY ENDPOINTS

Using the efficacy analysis set, the estimate of local control rate, intrahepatic progression free survival, and overall survival, will be plotted using Kaplan-Meier curve and reported with median survival and 95% CI if available. Using the same efficacy analysis set, the proportion of participants that proceed to transplantation, will be measured and reported with 95% CI.

Non-classic RILD, liver toxicity defined as a  $\geq 2$  increase in CP score (**Appendix A**), and liver toxicity per CTCAE v5.0, will be estimated along with an exact CI using the safety analysis set.

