### **9.4 HANDLING OF MISSING DATA**

Every attempt will be made to obtain data at the defined time points as described in the primary and secondary endpoints. For time points that have no data, we will evaluate whether or not the other time points can be used to fulfill the primary and secondary data. If the data are not sufficient to analyze specific endpoints, the participant's data may be excluded entirely or partially, depending on the specific endpoints in question and in consultation with the biostatistician. No missing data will be imputed. Whenever possible, all available data will be included in the analysis. A sample size for each analysis will be clearly stated along with the reason for exclusion, if any participant is excluded from the analysis due to missing data.

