## APPENDIX A: CHILD-TURCOTTE PUGH SCORE

The Child-Turcotte-Pugh (CP) scoring system utilizes the serum bilirubin, serum albumin, prothrombin time (PT)/ international normalized ratio (INR), degree of ascites and degree of hepatic encephalopathy and assigns 1–3 points for each variable. Patients are divided into three classes based on total points with  $\leq 6$ , 7–9, and  $\geq 10$  points representing Child's class A, B, and C, respectively.

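### Liver-related death is not an event in the RILD and Child-Pugh-rise proportions, so a participant who dies of liver failure without a qualifying assessment lowers both rates

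*Combined protocol and SAP*

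**What the plan says.** - **Definition.** Section 3.2.2 (endpoint 6) gives "Incidence of non-classic RILD, defined as grade 4 aspartate aminotransferase or alanine aminotransferase elevation, or an increase in CP score of" at least 2, between 1 week and 3 months after SBRT ends. Section 6.1.6.1 and the synopsis agree. None of them includes death or hepatic failure.
- **Analysis.** Under section 9.2.3, non-classic RILD, the CP rise and CTCAE liver toxicity "will be estimated along with an exact CI using the safety analysis set". Section 9.1 makes that set everyone from the first fraction onward.
- **Schedule.** Section 6.8, footnote B: "Follow-up assessment to occur 6 weeks following completion of SBRT then every 3 months up to 2 years post SBRT therapy". The follow-up window is plus or minus 4 weeks. Hematology, biochemistry and coagulation are marked at screening and follow-up only. Under section 6.5, follow-up stops at hospice enrollment or death.
- **Other sources of data.** Section 6.1.6 calls for CTCAE grading and "quantifying current Child-Pugh score to assess risk of RILD" at each visit. On unscheduled visits, section 6.7 says: "Any assessments performed (e.g., laboratory or clinical assessments) at those visits should be recorded in the CRF". Appendix A counts "degree of ascites and degree of hepatic encephalopathy and assigns 1–3 points for each variable" alongside the three laboratory items.
- **Missing data.** Section 9.4 imputes nothing. Where data are insufficient, it says a participant's "data may be excluded entirely or partially, depending on the specific endpoints in question", in consultation with the biostatistician and with the number analyzed and the reason stated.

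No section says how RILD or CP rise is classified for someone who dies before being assessed.

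**The concern.** Both proportions depend on an assessment that shows the deterioration. The people most likely to miss it are those who deteriorate fastest: they die, or go to hospice and leave scheduled follow-up, before the one visit at which laboratory values are due. The missingness is then related to the outcome being measured. A liver death with no qualifying assessment either stays in the denominator without being an event or is removed from the analysis. Both move the reported rate down, away from the hepatic harm it is meant to describe. Section 1.3 says the pilot is to feed the design of a larger multi-institutional trial, so a toxicity rate that omits these participants would be carried forward.

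**Working it through.** **No stated figure to reproduce.** The plan gives no design figure for RILD. Its only one is the sample size of 15 (section 9.3.1), which concerns dosimetric ineligibility. At a 20% probability, ln(0.05)/ln(0.80) = 13.43, so 14 suffice, and 15 give 1 − 0.80^15 = 96.5%. That figure reproduces and does not depend on this point.

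**Scheduled laboratory visits inside the window.** Three months is 3 × 365.25/12/7 = 13.0 weeks.

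- First follow-up: 6 ± 4, so weeks 2 to 10. Inside the window.
- Second follow-up, 3 months after the first: 6 + 13.0 = 19.0, with window 15.0 to 23.0. Outside.

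Only one scheduled visit qualifies. If the 3-monthly visits were instead counted from the end of SBRT, the next would fall at week 13.0, on the edge of the window. That would not help a participant who dies before week 6.

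**Effect on the rate.** Assume 15 participants start SBRT, x have measured RILD, and one more dies of liver failure with no qualifying data. The intervals are exact (Clopper-Pearson) 95%.

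| Handling of the death, x = 3 | Rate | 95% CI |
|---|---|---|
| Counted as an event | 4/15 = 26.7% | 7.8 to 55.1 |
| Definition not met, kept in denominator | 3/15 = 20.0% | 4.3 to 48.1 |
| Excluded under 9.4 | 3/14 = 21.4% | 4.7 to 50.8 |

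For general x:

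- Left as a non-event: the loss is 1/15 = 6.7 points.
- Excluded: the loss is (x+1)/15 − x/14 = (14 − x)/210, which is 5.7 points at x = 2 and 4.3 points at x = 5.

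With two such deaths and x = 3, the results are 5/15 = 33.3% (11.8 to 61.6) if counted, 3/15 = 20.0% if left as non-events, and 3/13 = 23.1% (5.0 to 53.8) if excluded.

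**How often could it happen?** The documents do not say. A loose guide is all-cause death before the 6-week visit. Assume exponential survival with the 17.0-month median that section 1.2.1 cites for CP-B patients, counted from the first fraction with about 10 days of treatment. The time is (6 + 10/7) weeks = 1.71 months, so 1 − 0.5^(1.71/17) = 6.7%, or 1.0 of 15. Medians of 12 and 24 months give 9.4% (1.4 of 15) and 4.8% (0.7 of 15). These are not counts of unmeasured liver deaths: not every death is hepatic, some participants will have unscheduled data, and the inclusion criterion of life expectancy above 12 weeks should lower the figures. Enrollment of CP-C patients could raise them.

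**Coverage by the CTCAE endpoint.** Synopsis secondary endpoint 7 uses the same window, 1 week to 3 months after SBRT. A fatal hepatic event in that window can be recorded there as grade 5. A liver death during SBRT, or in the first week after it, falls outside both endpoint windows.

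**The case against.** The strongest reply is that the gap is narrow.

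- A laboratory value is not strictly needed. Encephalopathy going from absent to severe, or a one-step rise in both ascites and encephalopathy, adds 2 CP points on clinical grounds. Unscheduled and hospital assessments can qualify.
- Exclusion under section 9.4 is conditional and must be reported with its reason, so it would be visible.
- Fatal liver toxicity has other outlets. "Adverse events will be monitored from the time the participant signs the Consent Form up until 3 months following SBRT", death is a serious adverse event, overall survival is an endpoint, CTCAE liver toxicity is analyzed in the same safety set, and section 8.7 pauses the study for a death suspected to be related to SBRT.
- The RILD definition comes from a cited source, and altering it would reduce comparability. Section 1.4.1 also warns that treatment toxicity is hard to separate from natural decline.

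All of this stands, and it limits the point to liver deaths with no qualifying data of any kind in the window. It does not remove the point: the other outlets record the death but leave the RILD and CP-rise proportions as they were. The comparability argument bears on the form of the fix, which should leave the definition alone.

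A reader might infer that the plan instructs that such a death be coded as absence of RILD. It does not. That coding follows from applying the definition literally; only exclusion is expressly permitted.

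**Conclusion.** The point holds as a gap in the definition and the missing-data rule. Taken literally, sections 3.2.2, 9.2.3 and 9.4 lower the RILD and CP-rise proportions whenever a participant dies of liver failure without a qualifying assessment. Each such death costs 6.7 points if left as a non-event and 4.3 to 5.7 points if excluded, assuming 15 treated and 2 to 5 measured cases. Against exact intervals about 44 to 47 points wide in the x = 3 example, the shift is modest. Its direction is fixed; its frequency is unknown.

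Two stronger readings are not supported. One is that the worst hepatic outcome vanishes from toxicity reporting: the CTCAE endpoint, serious adverse event reporting and the pause rule can capture it, apart from the endpoint gap before week 1. The other is that the rate would fail or pass a benchmark: section 8.4.1 lists 20-30% as a reported range, but no comparison with it is planned and the synopsis states there is no formal hypothesis test.

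**What to change.** Keep the cited RILD definition and its proportion, and add the following.

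1. In section 9.2.3, report the proportion with RILD (and likewise CP rise of at least 2) or liver-related death, from the first fraction to 3 months after the last. Give an exact CI and use the full safety set as denominator. Starting at the first fraction closes the gap before week 1.
2. In section 9.4, state that participants who die of liver-related causes before assessment may not be excluded from this proportion.
3. State that all scheduled and unscheduled CP and laboratory data are used.
4. Show assessment-based events and deaths separately.

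The sample size and visit schedule do not change. Adverse events are already collected from consent to 3 months, with description and relationship to treatment (sections 6.1.6 and 8.5), so the addition is mainly a rule for calling a death liver-related. The costs are a protocol amendment with the approvals in section 12.5, and the inclusion of some deaths from natural decline, which the separate display makes visible.

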### 3.2.3 EXPLORATORY ENDPOINT

Endpoint	Start	End
QoL scores for QLQ-C30 questionnaire		Death or 2-years after last SBRT dose, whichever occurs first
QoL scores for Functional Assessment of Cancer Therapy-Hepatobiliary (FACT-Hep) questionnaire	Screening	
Proportion of histopathologic changes in irradiated tumor sites relative to uninvolved liver tissue	Transplantation	Transplantation

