Secondary Endpoints	
 
1. Incidence of progressive disease within or at the planned tumor volume (PTV) margin (i.e. local control)
 
2. Incidence of progressive disease within any section of the liver, including the PTV (e.g. intrahepatic disease free survival)
 
3. Incidence of progressive disease outside of the liver (e.g. extrahepatic disease free survival)
 
4. Overall Survival
 
5. Proportion of participants that proceed to transplantation
 
6. Incidence of non-classical radiation-induced liver disease (RILD), defined as grade 4 aspartate aminotransferase or alanine aminotransferase elevation, or an increase in CP score of <math>\geq 2</math> within 1 week to 3 months after completing SBRT.
 

	7. Incidence of liver toxicity per CTCAE v5.0 within 1 week to 3 months after completing SBRT.
Exploratory Endpoints	
 
1. QoL scores for EORTC QLQ-C30 questionnaire
 
2. QoL scores for Functional Assessment of Cancer Therapy-Hepatobiliary (FACT-Hep) questionnaire
 
3. At time of transplantation, histopathologic changes in irradiated tumor sites relative to uninvolved liver tissue will be assessed
 

Number of Participants	15
Duration of Therapy	SBRT will be administered as 5 fractions every other day (~10 day)
Duration of Follow Up	Time of progression, or transplantation, or 2-years after last SBRT dose, whichever occurs first
Key Inclusion Criteria	
 
1. Participants aged <math>\geq 18</math> years
 
2. Patient diagnosed with HCC and recommended for LTX
 
3. Meets clinical criteria for eligibility for SBRT to the target lesion
 
4. Childs-Pugh Class B8 or higher
 
5. Eastern Clinical Oncology Group performance status <math>\leq 2</math>
 
6. Safe radiation treatment planning parameters that adhere to all organs at risk constraints per section 5.1 of the protocol. If normal organs at risk constraints (including at least 700cc of uninvolved liver) are unable to be met at the lowest dose modification (30 Gy in 5 fractions), the patient is deemed ineligible for SBRT and deemed a screen failure.
 

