In a recent retrospective study, Nabavizadeh et al reported on their single institution experience using SBRT or hypofractionated radiation therapy (AHRT) to treat 146 HCC patients with varying degrees of cirrhosis. The cohort included 51 patients with CP-B8 or higher cirrhosis (34% of entire cohort). Within this cohort, only a third of all patients experienced toxicity, defined as a CP elevation of 2 or more within 6 months of RT. These findings are comparable with other reports. Notably, the authors did not identify a statistically significant difference between rates of toxicity when comparing patients with CP-B8 or higher baseline cirrhosis to those with CP-A or B7 cirrhosis. Thirteen patients in the cohort with CP-B8 or higher cirrhosis eventually underwent LTX; suggesting that radiotherapy affords localized disease control for these patients awaiting transplantation. In this regard, the authors further observed that the 1- and 2-year local control (LC) rates were greater significantly better among patients receiving SBRT compared to those given AHRT (1-year LC 97% vs 72%,  $P <.0001$ ; 2-year LC 94% vs 65%,  $P <.0001$ ).

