## 2.3 EXPLORATORY OBJECTIVES

Assess quality of life in HCC patients with advanced cirrhosis following liver SBRT. Examine SBRT-related histopathologic changes in explanted livers of patients with advanced cirrhosis.

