#### **6.5 FOLLOW-UP**

Participants will be followed and disease assessments will take place 6 weeks following completion of SBRT, then every 3 months up until enrollment on hospice or death, or 2 years from time of last SBRT dose, whichever occurs first. Follow-up visits will be consistent with standard of care, and assessments are listed in Section 6.8. Any participants removed from protocol therapy for unacceptable AE(s) will be followed until resolution or stabilization of the AE.

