#### 9.2.4 ANALYSIS OF THE EXPLORATORY ENDPOINT

The QoL scores will be recorded over time (See Sections 6.1.8 and 6.8) using the EORTC QLQ-C30 and FACT-Hep questionnaires. Summary of QoLs and its change over time will be presented graphically using box plot and spaghetti plot, in addition to a summary table of QoL over time. No hypothesis testing is planned for QoL.

Descriptive statistical analysis, utilizing the efficacy analysis set, will be used to measure the proportion of histopathologic changes in irradiated tumor sites relative to uninvolved liver tissue will be measured.

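### By-visit quality-of-life summaries do not separate scores before and after transplantation, and the synopsis and body text disagree on whether follow-up continues past it

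*Combined protocol and SAP*

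**What the plan says.** The exploratory objective in section 2.3 reads "Assess quality of life in HCC patients with advanced cirrhosis following liver SBRT". The documents describe the QoL window and its analysis in several places:

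- **Section 3.2.3:** both questionnaires run from screening to "Death or 2-years after last SBRT dose, whichever occurs first".
- **Section 6.5:** visits take place at 6 weeks, "then every 3 months up until enrollment on hospice or death, or 2 years from time of last SBRT dose, whichever occurs first".
- **Section 6.8, footnote B** (attached to both questionnaires): "Follow-up assessment to occur 6 weeks following completion of SBRT then every 3 months up to 2 years post SBRT therapy".
- **Section 4.7:** progression can take a participant off study. Transplantation is not listed.
- **Synopsis, duration of follow-up:** "Time of progression, or transplantation, or 2-years after last SBRT dose, whichever occurs first".
- **Section 3.2.2, for contrast:** the progression endpoints and the transplanted proportion end at "Time of progression, transplantation, death or 2-years after last SBRT dose, whichever occurs first". Overall survival runs on to death or 2 years.
- **Section 9.2.4:** "Summary of QoLs and its change over time will be presented graphically using box plot and spaghetti plot", with a summary table over time and no hypothesis test. Transplantation is not mentioned for QoL.
- **Section 9.4:** no imputation. The sample size of each analysis is stated, with reasons for any exclusion due to missing data.

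**The concern.** Transplantation is the event this trial is meant to bridge to. Every participant must be listed or recommended for listing (section 4.1), so it is expected during QoL follow-up. After it, the participant no longer has the liver that the objective is about.

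Under the body text, questionnaires continue and each later visit mixes two groups. Deaths and hospice entries meanwhile remove other participants without imputation, so the mix can shift towards recipients as time passes. A by-visit display would then partly track who was transplanted and who was lost, as well as any effect of SBRT. If recipients score better than those still waiting, a decline in the latter is diluted. If recipients score worse, the distortion runs the other way.

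Under the synopsis, post-transplant scores would not exist. Recipients would instead leave the by-visit rows at transplantation, which is a selective loss that section 9.2.4 does not address either. Each reading needs a stated rule.

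**Working it through.** The plan gives no QoL sample size, standard deviation or expected change, so it has no QoL figure to reproduce. The check below shows how large the mixing could be under the body text.

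**Inputs from the documents (section 1.2.1)**
- Transplanted share: the retrospective series had 51 patients with CP-B8 or higher, and "Thirteen patients in the cohort with CP-B8 or higher cirrhosis eventually underwent LTX". So p = 13/51 = 0.255 (exact 95% CI 14.3% to 39.6%), or 15 × 0.255 = 3.8, about 4 of 15.
- Survival: median 17.0 months in the CP-B patients of the cited phase 1-2 trial, applied here to those not transplanted.

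**Assumptions not in the documents**
- All transplants fall in year 1, and 90% of recipients are alive at both 12 and 24 months.
- Survival is exponential, and every survivor returns a questionnaire.
- Mean change is -10 points in untransplanted participants, and g = 0 or +10 in recipients.

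**Recipients' share of scores at month t**

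share(t) = 0.9p / [0.9p + (1 - p) × exp(-t ln 2 / 17)]

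- Numerator: 0.9 × 0.2549 = 0.2294.
- 12 months: 0.7451 × 0.6131 = 0.4568, so the share is 0.2294 / 0.6862 = 0.334.
- 24 months: 0.7451 × 0.3759 = 0.2801, so the share is 0.2294 / 0.5095 = 0.450.

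**Change seen when the groups are combined** = -10 × (1 - share) + g × share

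| Month | Share | g = 0 | g = +10 |
|---|---|---|---|
| 12 | 0.334 | -6.7 | -3.3 |
| 24 | 0.450 | -5.5 | -1.0 |

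Untransplanted participants alone would show -10.

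**Sensitivity**
- *Number transplanted.* With 2 to 6 of 15, roughly the exact interval, the share runs from 18% to 49% at 12 months and from 27% to 61% at 24 months.
- *Timing.* Suppose transplants are spread evenly over 24 months and those awaiting a later transplant are alive. The 12-month share is then 0.1147 / (0.1147 + 0.1275 + 0.4568) = 0.164. The combined change is -8.4 for g = 0 and -6.7 for g = +10.
- *No deaths.* With 11 untransplanted and 4 transplanted all contributing, the change is -110/15 = -7.3 for g = 0 and (-110 + 40)/15 = -4.7 for g = +10.
- *Gain needed to cancel the fall.* 10 × (1 - share)/share gives 19.9 points at 12 months and 12.2 at 24 months in the base case. With no deaths it is 110/4 = 27.5.

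**The case against.** **A transplantation rule exists.** A reader might infer that the plan has none. The synopsis does end follow-up at transplantation, so that inference fails. The defect is a contradiction between the synopsis and sections 3.2.3, 6.5 and 6.8, together with silence in section 9.2.4. The synopsis cannot settle the matter alone, because overall survival in section 3.2.2 plainly runs past transplantation.

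**No averaging is specified.** Section 9.2.4 names no mean, and a spaghetti plot of about 15 people shows each course individually. This stands, so the combined means above are only a yardstick. Box plots and a table by visit would still put everyone present into one distribution, and nothing says transplantation will be marked on the individual lines.

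**The inputs are borrowed.** The 17-month median covers all CP-B patients in another trial, not CP-B8 or higher and not untransplanted patients. The 13 of 51 were transplanted at unstated times, and the series is not described as wholly listed. The QoL changes are invented for illustration. A reader might go on to infer that a decline would be hidden or would appear as an improvement. That needs a recipient gain above about 12 to 20 points even in the base case: an assumed +15 gives -1.6 at 12 months and +1.3 at 24 months. It is one scenario, and the documents supply nothing to support it over the others.

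**The objective may cover the whole course.** Enrolled patients with advanced cirrhosis can be followed through transplantation, since that is the intended success. Restricting the endpoint to pre-transplant scores would drop those successfully bridged. This is a fair estimand argument, so the fix should separate the display without requiring a pre-transplant-only endpoint.

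**Section 9.4 already promises sample sizes.** It does, but not by transplant status at each visit.

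**Conclusion.** The concern holds as an unresolved contradiction plus a gap in the analysis text. Under sections 3.2.3, 6.5 and 6.8, later QoL summaries combine post-transplant scores with scores from participants still waiting, and a decline in the latter could be diluted. The direction depends on recipients scoring better than those waiting.

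The amount is unknown. The illustrative base case puts recipients at about one third of scores at 12 months and just under half at 24 months. The 12-month share falls to about 16% if transplants come later. The 6-week visit is little affected. Because QoL is exploratory, descriptive and tied to no decision rule, this is a minor-to-moderate point. It is still worth correcting, because the correction is cheap and the pilot is meant to inform a larger trial.

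**What to change.** 1. Reconcile the end of QoL follow-up across the synopsis and sections 3.2.3, 4.7, 6.5 and 6.8. State explicitly what happens to the questionnaires at transplantation, progression and hospice entry.
2. In section 9.2.4, present by-visit change from screening separately for questionnaires completed before and after transplantation. A summary of all participants can be kept as an option.
3. Mark the time of transplantation on each line of the spaghetti plots.
4. Under each visit, state the numbers contributing, transplanted, dead and in hospice. If follow-up is settled as ending at transplantation, these counts are still needed to show why the rows shrink.

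Cost: the sample size stays at 15, the questionnaires are already scheduled, and section 3.1 already records time to transplantation, so no new assessment is needed. The wording change is a protocol revision that needs CRRC and IRB approval under section 12.5. The statistical drawback is small groups at later visits once the scores are split.
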